12. Reports habitually consuming more than 14 drinks containing alcohol per week (females) or more than 21 drinks containing alcohol per week (males), or unwilling to limit alcohol intake to 2 or fewer drinks per day or forego alcohol within 3 hours before bedtime for the duration of his/her participation in the study

13. Known to be human immunodeficiency virus (HIV) positive
14. Active viral hepatitis (B or C) as demonstrated by positive serology at Screening
15. A prolonged QT/QT interval corrected by Fridericia's formula (QTcF >450 ms) as demonstrated by a repeated ECG at Screening (repeated only if initial ECG indicates a QTcF interval >450 ms) (revised per Amendment 03)
16. Current evidence of clinically significant disease (eg, cardiac; respiratory including chronic obstructive pulmonary disease, acute and/or severe respiratory depression; severe hepatic insufficiency; gastrointestinal; renal including severe renal impairment; neurological [including subjects who lack capacity and/or whose cognitive decline indicates disorientation to person/place/time and/or situation] or psychiatric disease or malignancy within the past 5 years [other than adequately treated basal cell carcinoma]) or chronic pain that in the opinion of the investigator(s) could affect the subject's safety or interfere with the study assessments. Subjects for whom a sedating drug would be contraindicated for safety reasons because of the subject's occupation or activities are also excluded. (revised per Amendment 01)
17. Comorbid nocturia resulting in frequent need to get out of bed to use the bathroom during the night
18. Any history of a medical or psychiatric condition that in the opinion of the investigator(s) could affect the subject's safety or interfere with the study assessments
19. Any suicidal ideation with intent with or without a plan at Screening or Study Baseline or within 6 months of Study Baseline (ie, answering "Yes" to questions 4 or 5 on the Suicidal Ideation section of the eC-SSRS)
20. Any suicidal behavior in the past 10 years (per the Suicidal Behavior section of the eC-SSRS) (revised per Amendment 03)
21. Scheduled for major surgery during the study (revised per Amendment 03)
22. Used any prohibited prescription or over-the-counter concomitant medications within 1 week or 5 half lives, whichever is longer, before the 1st dose of study medication (Run-In Period). (A list of prohibited or limited concomitant medications is presented in [Appendix 3.](#))

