Abnormal ECG (QTc) results, if not otherwise considered part of a clinical symptom that is being reported as an AE, should be considered an AE if the QTcF interval is more than 450 ms and there is an increase of more than 60 ms from baseline. Any ECG abnormality that the investigator considers as an AE should be reported as such. (revised per Amendment 03)

It is the responsibility of the investigator to review the results of the C-SSRS in all subjects and determine if any result constitutes an AE. Medical and scientific judgment should be exercised in deciding whether an isolated suicidality rating scale response should be classified as an AE (see [Section 9.5.1.5.7](#) for a description of the eC-SSRS).

AEs in clinical investigation subjects include any change in the subject's condition. This includes symptoms, physical findings, or clinical syndromes. All AEs encountered during the clinical study will be reported on the electronic CRF (eCRF).

All AEs must be followed for 28 days after the subject's last dose, or until resolution, whichever comes first. All SAEs must be followed to resolution or, if resolution is unlikely, to stabilization.

Every effort must be made by the investigator to categorize each AE according to its severity and its relationship to the study treatment.

ASSESSING SEVERITY OF ADVERSE EVENTS

AEs will be graded on a 3-point scale (mild, moderate, severe) and reported in the detail indicated on the CRF. The definitions are as follows:

- | | |
|----------|--|
| Mild | Discomfort noticed, but no disruption of normal daily activity |
| Moderate | Discomfort sufficient to reduce or affect normal daily activity |
| Severe | Incapacitating, with inability to work or to perform normal daily activity |

The criteria for assessing severity are different than those used for seriousness (see [Section 9.5.1.5.2](#) for the definition of an SAE).

ASSESSING RELATIONSHIP TO STUDY TREATMENT

Items to be considered when assessing the relationship of an AE to the study treatment are:

- Temporal relationship of the onset of the event to the initiation of the study treatment
- The course of the event, especially the effect of discontinuation of study treatment or reintroduction of study treatment, as applicable
- Whether the event is known to be associated with the study treatment or with other similar treatments
- The presence of risk factors in the study subject known to increase the occurrence of the event

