- d: Visits 4, 5, and 6 are to be conducted within ± 4 days of the schedule. Visits 7 through 15, and EOS to be done within ± 7 days of the schedule. (revised per Amendments 01 and 03)
- e: The site will telephone the subject to assess AEs, to record concomitant medications and to review the sleep diaries. If any AE is clinically significant and requires follow-up, a clinic visit should be arranged (Unscheduled Visit).
- f: The Run-In Period may start between Day -17 and Day -14 and must continue for approximately 14 consecutive days and a maximum of 17 days. (revised per Amendment 01)
- g: Defined as a calendar month.
- h: Inclusion and exclusion criteria to be evaluated at visits other than or in addition to Visit 1 are listed in [Appendix 2](#) (revised per Amendment 01).
- i: Sleep Disorders Screening Battery comprises: STOPBang, International Restless Legs Scale, and Epworth Sleepiness Scale. (revised per Amendments 01 and 03).
- j: A full physical examination will be carried out at Screening and EOS (ET at the discretion of the investigator) and will include a brief neurological examination. A brief physical examination will be carried out at other visits.
- k: The ECG should be repeated if an abnormality is observed.
- l: If subject has a normal ECG baseline reading, but during any visit thereafter the QT is measured as >450 ms, 3 consecutive ECGs separated by 5 to 10 minutes will be performed to confirm the abnormality.
- m: Female subjects of child-bearing only.
- n: Urine drug test to be conducted at Unscheduled Visits at the discretion of the investigator and at ET only for subjects who withdraw because of an Adverse Event.
- o: Viral screening for hepatitis B (HBsAg) and hepatitis C (HCV antibody IgG) will be conducted.
- p: Clinical laboratory tests include hematology, blood chemistry, and urinalysis.
- q: Subjects should complete the Sleep Diary, within 1 hour of waketime, each day throughout the study until EOS. Sleep diaries should be reviewed for eligibility: for the 7 consecutive days immediately before Visit 2, and for the Run-In Period at Visit 3. Thereafter, the Sleep Diary should be reviewed for completeness

-
- once a month. (revised per Amendment 03)
- r: Study drug compliance (tablet count) will be carried out at each clinic visit from Visit 3a through Visit 15. (revised per Amendments 01 and 03)

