9.7.1.8.5 ELECTROCARDIOGRAMS

Descriptive statistics for ECG parameters and changes from Study Baseline (Safety Analysis Set) will be presented by treatment group and visit. This will also be repeated for the 12-month LEM exposure (On-Treatment Safety Analysis Set), summarized by treatment group and duration of exposure. (revised per Amendment 06)

Shift tables will present changes from Study Baseline in ECG interpretation (categorized as normal and abnormal) by time point. (revised per Amendment 03)

For each subject, the maximum observed QTcF, the corrected QT interval calculated using Bazett's formula (QTcB), and the maximum prolongation from Study Baseline in QTcF will be compiled. Categorical analyses of subjects (number and percent) with maximum observed QTcF values >450 ms, >480 ms, and >500 ms and maximum prolongations (from Study Baseline) in QTcF >30 ms and >60 ms will be presented by treatment group and by time point. Categorical analyses of subjects (number and percent) with maximum observed PR values >220 ms, and QRS values >120 ms will be presented by treatment group and by time point. This will also be repeated for the 12-month LEM exposure (On-Treatment Safety

Analysis Set), summarized by treatment group and duration of exposure. (revised per Amendment 06)

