LDA	longitudinal data analysis
LEM5	lemborexant, 5-mg dose
LEM10	lemborexant, 10-mg dose
LNH	low-normal-high
LS	least squares

Abbreviation	Term
MAR	missing at random
MCMC	Monte Carlo Markov Chain
MI	Multiple Imputation
MNAR	missing not at random
MedDRA	Medical Dictionary for Regulatory Activities
NREM	non-REM sleep
PAB	performance assessment battery
PBO	placebo
PD	pharmacodynamic
PGI	Patient Global Impression
PK	pharmacokinetic
PK/PD	pharmacokinetic/pharmacodynamic
PT	preferred term
QTcB	QT interval calculated using Bazett's formula
QTcF	QT interval corrected for heart rate by Fridericia's formula
SAE	serious adverse event
SAP	statistical analysis plan
SD	Standard deviation
SE	sleep efficiency
SOC	system organ class
SDSB	Sleep Disorders Screening Battery
sSE	subjective sleep efficiency
sSOL	subjective sleep onset latency
sTIB	subjective time in bed
sTST	subjective total sleep time
sWASO	subjective wake after sleep onset
T-BWSQ	Tyrer Benzodiazepine Withdrawal Symptom Questionnaire
TEAE	treatment-emergent adverse event
TIB	time in bed
TST	total sleep time

Abbreviation	Term
US	United States
VAS	visual analog scale
WASO	wake after sleep onset
WBC	white blood cells
WPAI-GH	Work Productivity and Activity Impairment Questionnaire – General Health
TLG	tables, listings, and graphs

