3.6.6 Electrocardiograms

Descriptive statistics for ECG parameters and changes from Study Baseline (Safety Analysis Set) will be presented by treatment group. This will also be repeated for the 12-month LEM exposure (On-Treatment Safety Analysis Set), summarized by treatment group and duration of exposure. Shift tables will present changes from Study Baseline in ECG interpretation (categorized as normal; abnormal, not clinically significant; and abnormal, clinically significant) by time point.

In addition, maximum postbaseline measurement will also be tabulated separately for the Period 1 and 12-month LEM exposure by treatment group as follows:

- Number and percentage of subjects with QTcF of >450 msec, and >500 msec during the treatment
- Number and percentage of subjects with a QTcF increment of >30 msec, and >60 msec from the baseline visit.
- Number and percentage of subjects with PR of >220 msec
- Number and percentage of subjects with QRS of >120 msec

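### The on-treatment trigger for three confirmatory ECGs is set on QT rather than QTcF, so above 60 bpm some QTcF readings over 450 ms do not trigger it

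*Protocol*

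**What the plan says.** Two footnotes to Table 3 (Protocol 9.5.2) govern repeat ECGs. Footnote k, on the whole 12-lead ECG row, is general: "The ECG should be repeated if an abnormality is observed". Footnote l is attached to each of the six scheduled post-baseline ECGs (Months 1, 3, 6, 9 and 12, and End of Study). It applies to subjects whose baseline ECG was normal, and is met when "the QT is measured as >450 ms, 3 consecutive ECGs separated by 5 to 10 minutes will be performed to confirm the abnormality".

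The other places where 450 ms appears as a limit all name QTcF:

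- Protocol 9.3.2, exclusion 15: the screening ECG is "repeated only if initial ECG indicates a QTcF interval >450 ms".
- Protocol 9.5.1.5.1: an abnormal ECG not already part of a reported event is "considered an AE if the QTcF interval is more than 450 ms and there is an increase of more than 60 ms from baseline".
- Protocol 9.7.1.8.5: the categorical analyses count subjects with "maximum observed QTcF values >450 ms, >480 ms, and >500 ms".
- SAP 3.6.6: "Number and percentage of subjects with QTcF of >450 msec, and >500 msec during the treatment".

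The protocol's abbreviation list (Section 4) has separate entries for QTc, QTcB and QTcF. The SAP's list defines QTcF as "QT interval corrected for heart rate by Fridericia's formula".

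**The concern.** QT shortens as heart rate rises, so a fixed limit on QT corresponds to a different QTcF at every rate except 60 bpm. Footnote l is the only repeat rule during treatment that gives a threshold, a number of tracings and a spacing. If it is applied as worded, a subject with a faster pulse can have a QTcF over 450 ms, or even meet the adverse event rule, without the three tracings being required. A subject with a slow pulse can be sent for three tracings with a QTcF well under 450 ms.

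The closest parallel is the screening rule, which is also a repeat-ECG trigger at 450 ms but on QTcF. The documents give no reason for using a different measure after baseline. What is at stake is the confirmation of QT prolongation on treatment. A confirmation not done at the visit cannot be recreated later.

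**Working it through.** The plan gives no figure of its own to reproduce here, so the check converts between the two scales.

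**Inputs.** The trigger is QT >450 ms (Table 3, footnote l). The comparison limits are QTcF 450, 480 and 500 ms (Protocol 9.7.1.8.5). The adverse event rule is QTcF >450 ms with a rise >60 ms (Protocol 9.5.1.5.1). Both documents name Fridericia's formula but do not write it out, so the standard form is assumed. Neither document gives a distribution of heart rates, so the rates below are illustrative.

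**Formula.** QTcF = QT / RR^(1/3), with RR = 60 / heart rate in seconds.

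**Step 1: the QTcF at which footnote l starts to fire (QT = 450 ms), and the QT that equals QTcF 450 ms.**

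| Heart rate (bpm) | RR (s) | QTcF when QT = 450 ms | QT when QTcF = 450 ms | QTcF above 450 ms with no trigger |
|---|---|---|---|---|
| 50 | 1.200 | 423.5 | 478.2 | none |
| 55 | 1.091 | 437.1 | 463.2 | none |
| 60 | 1.000 | 450.0 | 450.0 | none |
| 65 | 0.923 | 462.2 | 438.2 | up to 462.2 |
| 70 | 0.857 | 473.7 | 427.5 | up to 473.7 |
| 75 | 0.800 | 484.7 | 417.7 | up to 484.7 |
| 80 | 0.750 | 495.3 | 408.9 | up to 495.3 |
| 90 | 0.667 | 515.1 | 393.1 | up to 515.1 |

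The untriggered band opens at 60 bpm and widens with rate. Below 60 bpm the error reverses: at 50 bpm three ECGs are required from a QTcF just above 423.5 ms.

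**Step 2: the heart rate above which a given QTcF is missed.** Setting QT = 450 ms and solving gives rate = 60 × (QTcF / 450)³.

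- QTcF 480 ms: 60 × (480/450)³ = 72.8 bpm.
- QTcF 500 ms: 60 × (500/450)³ = 82.3 bpm.

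**Step 3: can a reading meet the adverse event rule without triggering footnote l?**

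- QTcF 470 ms at 75 bpm: QT = 470 × 0.80^(1/3) = 436.3 ms, below 450 ms, so no trigger. With a baseline QTcF of 400 ms the rise is 70 ms, and the adverse event rule is met.
- QTcF 490 ms at 80 bpm: QT = 490 × 0.75^(1/3) = 445.2 ms, again no trigger. With any baseline QTcF below 430 ms the rise exceeds 60 ms, and the rule is met.

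**The case against.** The strongest reply is that QT in footnote l is loose wording for QTcF. All the other 450 ms limits are on QTcF, and the protocol's QT terms are not always tidy: exclusion 15 runs QT and QTcF together in one phrase. A site could read footnote l in that light, and then no band is missed. This is possible, but the protocol lists the corrected intervals under their own abbreviations and footnote l uses none of them. If QTcF was meant, the correction should be uncontroversial.

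Second, footnote k already calls for a repeat when an abnormality is seen, at any heart rate. That stands in part: a single repeat may well be done. Footnote k sets no threshold, number of tracings or spacing, so it does not guarantee the three-ECG confirmation.

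Third, nothing in the plan hangs on the three tracings. There is no QTc stopping rule, and neither the adverse event rule nor the maximum-QTcF tables require confirmation. This stands, and it limits the weight of the point.

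Fourth, footnote l applies only after a normal baseline ECG, and the examples need particular rates and baselines. This is also true. The baseline condition narrows the rule equally whichever interval is used, and the rate dependence follows from the formula rather than from the examples.

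The Amendment 03 entry in the revision history that moved exclusion 15 from QTc to QTcF does not list Table 3. That is compatible with an oversight but does not prove one.

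**Conclusion.** The concern holds. As written, footnote l sets its trigger on an uncorrected interval, out of line with the protocol's other 450 ms rules, and it gives a different answer from QTcF at every heart rate other than 60 bpm. The missed band reaches 474 ms at 70 bpm and 495 ms at 80 bpm, and can include readings that are adverse events by the protocol's own definition.

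This rests on the standard Fridericia formula and on sites applying the footnote literally. The heart rates are assumed, so the number of subjects affected cannot be estimated. The loss is the specified three-ECG confirmation. Prolonged QTcF readings still enter the adverse event assessment and the ECG tables. It should be corrected because the remedy is so small, but it does not threaten the trial's conclusions.

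**What to change.** In Table 3, footnote l, replace QT with QTcF, keep the 450 ms limit, and notify sites. The adverse event rule can keep its additional requirement of a rise above 60 ms, since a trigger for repeat tracings may reasonably be more sensitive than the definition of an event. The change removes both the missed band above 60 bpm and the over-triggering below it.

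The cost is one word in one footnote, a note to sites, and some extra repeat ECGs at rates above 60 bpm, partly offset by fewer at slow rates. No new procedure is introduced.

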9.5.3 Appropriateness of Measurements

Completion of sleep diaries by subjects is considered to be an appropriate method to measure changes in subjective sleep parameters, thereby allowing assessments of secondary efficacy in this study. The advantages of the electronic Sleep Diary to be used in this study include that the questions and instructional text have been adapted from sleep diaries that were developed by clinicians and researchers with expertise in insomnia disorder, and have undergone linguistic validation and cognitive debriefing to optimize their use in this study. The Sleep Diary will include questions to assess the subject's rating of sleep quality each night and sleepiness/alertness level in the morning.

The ISI has been widely used to evaluate the subjective impact of insomnia severity on psychosocial functioning, which is one type of daytime functioning impairment experienced by those with insomnia disorder. The FSS measures fatigue, which is another type of daytime impairment that is often a consequence of insomnia. This scale has been employed primarily in clinical trials of cognitive and behavioral treatments for insomnia disorder. Because the objectives of this study include assessing the response to lemborexant of both nighttime sleep and daytime impairment complaints, the ISI and the FSS will be evaluated for changes from baseline. The PGI-Insomnia, EQ-5D-3L and WPAI-GH will also be employed. These measures have been used in studies evaluating the impact of treatment for insomnia on patients' global perceptions of sleep quality and quality of life. Together these measures will provide a broad evaluation of the effects of lemborexant on each patient's sleep, daytime functioning, quality of life and productivity.

The safety assessments performed in this study, including clinical laboratory analyses, vital sign parameters, electrocardiograms, and assessment of AEs are standard evaluations to ensure subject safety. The C-SSRS, a standardized assessment required by regulatory authorities, will be used to evaluate any effects of lemborexant on suicidality. Additional safety-related assessments include evaluation of morning sleepiness and rebound insomnia, which will be measured using the validated Sleep Diary.

9.5.4 Reporting of Serious Adverse Events, Pregnancy, and Events Associated with Special Situations

9.5.4.1 Reporting of Serious Adverse Events

All SERIOUS ADVERSE EVENTS, regardless of their relationship to study treatment, must be reported on a completed SAE form by email or fax as soon as possible but no later than 24 hours after the time the investigator becomes aware of the event.

Serious adverse events, regardless of causality assessment, must be collected through the last visit and for 28 days after the subject's last dose. All SAEs must be followed to resolution or, if resolution is unlikely, to stabilization. Any SAE judged by the investigator to be related to the study treatment or any protocol-required procedure should be reported to the sponsor regardless of the length of time that has passed since study completion.

The detailed contact information for reporting of SAEs is provided in the Investigator Study File.

For urgent safety issues, please ensure all appropriate medical care is administered to the subject and contact the appropriate study team member listed in the Investigator Study File.

It is very important that the SAE report form be filled out as completely as possible at the time of the initial report. This includes the investigator's assessment of causality.

Any follow-up information received on SAEs should be forwarded within 24 hours of its receipt. If the follow-up information changes the investigator's assessment of causality, this should also be noted on the follow-up SAE form.

Preliminary SAE reports should be followed as soon as possible by detailed descriptions including copies of hospital case reports, autopsy reports, and other documents requested by the sponsor.

The investigator must notify his/her IRB/IEC of the occurrence of the SAE in writing, if required by their institution. A copy of this communication must be forwarded to the sponsor or the responsible CRO, to be filed in the sponsor's Trial Master File.

9.5.4.2 Reporting of Pregnancy and Exposure to Study Drug Through Breastfeeding

Any pregnancy in which the estimated date of conception is either before the last visit or within 28 days of last study treatment, or any exposure to study drug through breastfeeding during study treatment or within 28 days of last study treatment, must be reported.

If an adverse outcome of a pregnancy is suspected to be related to study drug exposure, this should be reported regardless of the length of time that has passed since the exposure to study treatment.

A congenital anomaly, death during perinatal period, an induced abortion, or a spontaneous abortion are considered to be an SAE and should be reported in the same time frame and in the same format as all other SAEs (see Reporting of Serious Adverse Events [[Section 9.5.4.1](#)]).

Pregnancies or exposure to study drug through breastfeeding must be reported by fax or email as soon as possible but no later than 24 hours after the time the investigator becomes aware of the pregnancy. The contact information for the reporting of pregnancies and exposure to study drug through breastfeeding is provided in the Investigator Study File. The Pregnancy Report Form must be used for reporting. All pregnancies must be followed to outcome. The outcome of the pregnancy must be reported as soon as possible but no later than 24 hours from the date the investigator becomes aware of the outcome.

A subject who becomes pregnant must be withdrawn from the study.

